## Table 14.3.2.1 Overall Incidence of Safety Events Safety Population

#### 7.3.3 Footnotes

Unless otherwise specified, footnotes will appear on all pages within the tables and listings as follows:

• Footnotes will be in the format of "Note: followed by 2 spaces, then the footnotes", as shown in the following example:

Note: SD = Standard Deviation; SEM = Standard Error of the Mean.

• Each line of a complete footnote should end with a period.

- When an abbreviation (e.g. AE, SAE, etc.) appears first time in the whole set of TFLs for a study, a footnote should be provided at least once; and it is up to the study statistician to decide whether there is a need to repeat the same footnote for the rest of TFLs.
- A footnote serves as a brief explanation/clarification /definition /concept of a flag symbol or a character, an abbreviation, a terminology, etc., that appears in or relates directly to the displayed content of a table/listing/figure.
- All footnotes will be at the lowest line of the page immediately above the footer. There will be one space between the last footnote and the footer.
- For Tables, first footnote will provide source listings and/or analysis datasets names for cross-referencing.

#### **7.3.4 Footer**

The following footer should appear at the very bottom of each page of a table, a listing, or a figure generated in SAS in the lower left corner:

Program: PGNAME.sas; Creation Date and Time: DDMMMYYYY HH:MM
Data Cutoff: DDMMMYY:HH:MM:SS – ADaM Generated MMM DD, YYYY

where PGNAME = SAS program name.

#### 7.4 Statistical Conventions

## 7.4.1 Statistics Reported

• Unless otherwise specified, the mean and median will be displayed to one more decimal place than the original value and the standard deviation to two more decimal places, while minimum and maximum will be reported in the format of the original data, e.g.:

Original: xx

Mean and median: xx.x

SD: xx.xx

Minimum and maximum: xx

- Descriptive statistics in this template include: Mean, Median, Standard Deviation (SD), Q1, Q3, and N. In addition, 95% CI will be presented when appropriate.
- Unless specified in the actual TFL shells for a study, all percentages will be rounded to 2 decimal places in all tables/figures/listings, with the exception of adverse events, which will be rounded to 1 decimal place. Rounding will take place after all calculations have been performed.

- Population summaries that include p-values will report the p-value to four decimal places with a leading zero (0.0001). All p-values reported on default output from statistical software (i.e., SAS® Software) may be reported at the default level of precision. P-values <0.0001 should be reported as <0.0001 not as 0.0000.
- Use of N versus n:
  - N = total number of subjects or subjects in the population.
  - n = total number of subjects or subjects in the specific category.

## 7.4.2 SAS Procedure Output

If appropriate, SAS procedure output may be formatted and saved as source for references and will be included in Appendix.

## 7.4.3 Tables Summarizing Categorical Data

The following specifications apply to tables that summarize categorical data:

- Percent of events should be left blank (including the parentheses) if the number of events is zero.
- If the categories of a parameter are ordered, then all categories between the maximum possible category and the minimum category will be included, even if n=0 for a given category between the minimum and maximum level for that parameter.
- If the categories are not ordered, then only those categories for which there is at least one subject represented will be included.
- A missing category will be added to any parameter for which information is not available for any subjects.

# 7.4.4 Subject Data Listings

In general, individual subject data listings should include all subjects with data. However, if a subject data listing includes only subjects who met a certain condition, and there were no subjects who met that condition, then a "message" will appear indicating that no subjects met the condition for inclusion in that listing.

# 9.1 Planned Tables, Listings, and Figures

**Tables and Figures:** 

Tables and Figures	:
Table 14.1.1.1	Screen Failure Summary (All Subjects)
Table 14.1.1.2	Subject Disposition (All Subjects)
Table 14.1.2	Protocol Deviations Part 3 (ITT Population)
Table 14.1.3.1	Demographics and Baseline Characteristics (ITT Population)
Table 14.1.3.2	Demographics and Baseline Characteristics in Part 2 (Safety Population)
Table 14.1.3.3	Demographics and Baseline Characteristics in Part 3 (Safety Population)
Table 14.1.4	Medical History (Safety Population)
Table 14.1.5.1	Multiple Sclerosis History (ITT Population)
Table 14.1.5.2	Multiple Sclerosis History (Safety Population)
Table 14.1.6.1	Spasticity History (ITT Population)
Table 14.1.6.2	Spasticity History (Safety Population)
Table 14.1.7.1	Prior Medications (Safety Population)
Table 14.1.7.2.1	Concomitant Medications Part 2 (Safety Population)
Table 14.1.7.2.2	Concomitant Medications – Anti-Spasticity Part 2(Safety Population)
Table 14.1.7.2.3	Concomitant Medications – Neurological Part 2 (Safety Population)
Table 14.1.7.3.1	Concomitant Medications Part 3 (Safety Population)
Table 14.1.7.3.2	Concomitant Medications – Anti-Spasticity Part 3 (Safety Population)
Table 14.1.7.3.3	Concomitant Medications – Neurological Part 3 (Safety Population)
Table 14.1.8	Physical Examination Results (Safety Population)
Table 14.1.9	Neurological Examination Results (Safety Population)
Table 14.1.10.1.1	Exposure Dose Levels Parts 1 and 2 (Safety Population)
Table 14.1.10.1.2	Acceptable Conversion Dose Levels at Week 6 Parts 1 and 2 (Safety Population)
Table 14.1.10.1.3	Dosing Compliance Parts 1 and 2 (Safety Population)
Table 14.1.10.2.1	Exposure Dose Levels Part 3 (Safety Population)
Table 14.1.10.2.2	Dosing Compliance Part 3 (Safety Population)
Table 14.2.1	Treatment Failure Rates (ITT Population)
Table 14.2.2	Subject Global Impression of Severity (ITT Population)
14010 14.2.2	Subject Global Impression of Severity (11 1 1 optimizion)
Table 14.2.5	Treatment Failure Rates by Gender (ITT Population)
Table 14.2.6	Treatment Failure Rates by Race (ITT Population)
Table 14.2.7	Treatment Failure Rates by Age Group (<65 or ≥65) (ITT Population)

Table 14.2.20	Time To Dropout in Part 3 (ITT Population)
Table 14.3.1.1.1	Overview of Adverse Events in Part 2 (Safety Population)
Table 14.3.1.1.2	Incidence of Treatment-Emergent Adverse Events in Part 2 (Safety Population)
	Incidence of Treatment-Emergent Adverse Events by Descending Order of Frequency
Table 14.3.1.1.3	of Preferred Terms in Part 2 (Safety Population)
Table 14.3.1.1.4	Incidence of Treatment-Emergent Adverse Events by Maximum Severity in Part 2 (Safety Population)
14010 14.5.1.1.4	Incidence of Treatment-Emergent Adverse Events by Highest Relationship in Part 2
Table 14.3.1.1.5	(Safety Population)
	Incidence of Treatment-Related Treatment-Emergent Adverse Events by Highest
Table 14.3.1.1.6	Relationship in Part 2 (Safety Population)
Table 14.3.1.1.7	Incidence of Treatment-Emergent Adverse Events Leading to Discontinuation in Part 2 (Safety Population)
14016 14.5.1.1./	Incidence of Treatment-Emergent Adverse Events by Gender in Part 2 (Safety
Table 14.3.1.1.8	Population)
Table 14.3.1.1.9	Incidence of Treatment-Emergent Adverse Events by Age Group in Part 2 (Safety
	Population)
Table 14.3.1.1.10	Incidence of Treatment-Emergent Adverse Events by Race in Part 2 (Safety
Table 14.3.1.1.11	Population) Incidence of Treatment-Emergent Adverse Events by Concomitant Medications in at
14010 14.5.1.1111	Least 20% of Subjects in Part 2 (Safety Population)
Table 14.3.1.1.12	Incidence of Treatment-Emergent Adverse Events by Medical Conditions Present in
	at Least 20% of Subjects at Screening in Part 2 (Safety Population)
Table 14.3.1.1.13	Incidence of Treatment-Emergent Adverse Events by Renal Function in Part 2 (Safety
	Population) Incidence of Treatment-Emergent Adverse Events by Dose at Earliest Onset in Part 2
Table 14.3.1.1.14	(Safety Population)
Table 14.3.1.2.1	Overview of Adverse Events by Treatment Group in Part 3 (Safety Population)
14010 1 1.0.1.2.1	Incidence of Treatment-Emergent Adverse Events by Treatment Group in Part 3
Table 14.3.1.2.2	(Safety Population)
	Incidence of Treatment-Emergent Adverse Events by Descending Order of Frequency
Table 14.3.1.2.3	of Preferred Terms by Treatment Group in Part 3 (Safety Population)
	Incidence of Treatment-Emergent Adverse Events by Maximum Severity by
Table 14.3.1.2.4	Treatment Group in Part 3 (Safety Population)

	Incidence of Treatment-Emergent Adverse Events by Highest Relationship by	
Table 14.3.1.2.5	Treatment Group in Part 3 (Safety Population)	
Table 14.3.1.2.6	Incidence of Treatment-Related Treatment-Emergent Adverse Events by Highest Relationship by Treatment Group in Part 3 (Safety Population)	
Table 14.3.1.2.7	Incidence of Treatment-Emergent Adverse Events Leading to Discontinuation by Treatment Group in Part 3 (Safety Population)	
Table 14.3.1.2.8	Incidence of Treatment-Emergent Adverse Events by Gender by Treatment Group in Part 3 (Safety Population)	
Table 14.3.1.2.9	Incidence of Treatment-Emergent Adverse Events by Age Group by Treatment Group in Part 3 (Safety Population)	
Table 14.3.1.2.10	Incidence of Treatment-Emergent Adverse Events by Race by Treatment Group in Part 3 (Safety Population)	
Table 14.3.1.2.11	Incidence of Treatment-Emergent Adverse Events by Concomitant Medications in at Least 20% of Subjects by Treatment Group in Part 3 (Safety Population)	
Table 14.3.1.2.12	Incidence of Treatment-Emergent Adverse Events by Medical Conditions Present in at Least 20% of Subjects at Screening by Treatment Group in Part 3 (Safety Population)	
Table 14.3.1.2.13	Incidence of Treatment-Emergent Adverse Events by Renal function by Treatment Group in Part 3 (Safety Population)	
Table 14.3.1.2.14	Incidence of Treatment-Emergent Adverse Events by Dose at Earliest Onset by Treatment Group in Part 3 (Safety Population)	
Table 14.3.2.1.1	Incidence of Treatment-Emergent Serious Adverse Events in Part 2 (Safety Population)	
Table 14.3.2.1.2	Incidence of Treatment-Related Treatment-Emergent Serious Adverse Events by Highest Relationship in Part 2 (Safety Population)	
Table 14.3.2.1.3	Incidence of Fatal Treatment-Emergent Serious Adverse Events in Part 2 (Safety Population)	
Table 14.3.2.2.1	Incidence of Treatment Emergent Serious Adverse Events by Treatment Group in Part 3 (Safety Population)	
Table 14.3.2.2.2	Incidence of Treatment-Related Treatment-Emergent Serious Adverse Events by Highest Relationship in Part 3 (Safety Population)	
Table 14.3.2.2.3	Incidence of Fatal Treatment-Emergent Serious Adverse Events in Part 3 (Safety Population)	
Table 14.3.4.1.1	Vital Signs in Part 2 (Safety Population)	
Table 14.3.4.1.2	Vital Signs in Part 3 (Safety Population)	
Table 14.3.4.1.3	Potentially Clinically Significant Vital Signs in Part 2 (Safety Population)	
Table 14.3.4.1.4	Potentially Clinically Significant Vital Signs in Part 3 (Safety Population)	
Table 14.3.4.2.1	Hematology Laboratory Assessments (Safety Population)	
Table 14.3.4.2.2	Hematology Laboratory Shift Table (Safety Population)	
Table 14.3.4.2.3	Number and Percentage of Subjects with a Possibly Clinically Significant (PCS) Hematology Results – Safety Population	
Table 14.3.4.3.1	Chemistry Laboratory Assessments (Safety Population)	
Table 14.3.4.3.2	Chemistry Laboratory Shift Table (Safety Population)  Number and Percentage of Subjects with a Possibly Clinically Significant (PCS)	
Table 14.3.4.3.3	Chemistry Results – Safety Population	
Table 14.3.4.4	Urinalysis Summary (Safety Population)	
Table 14.3.4.5.1	12-Lead Electrocardiogram Parameters in Part 2 (Safety Population)	
Table 14.3.4.5.2	12-Lead Electrocardiogram Parameters in Part 3 (Safety Population)	
Table 14.3.4.5.3	Clinical Interpretation and Categorical Results of 12-Lead Electrocardiogram in Part 2 (Safety Population)	
Table 14.3.4.5.4	Clinical Interpretation and Categorical Results of 12-Lead Electrocardiogram in Part 3 (Safety Population)	

Version 9.0

	C-SSRS Summary of Suicidal Ideation and Suicidal Behavior in Part 1 (Safety
Table 14.3.5.1	Population)
	C-SSRS Summary of Suicidal Ideation and Suicidal Behavior in Part 2 (Safety
Table 14.3.5.2	Population)
	C-SSRS Summary of Suicidal Ideation and Suicidal Behavior in Part 3 (Safety
Table 14.3.5.3	Population)

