#### 7 WITHDRAWAL AND REPLACEMENT RULES

#### 7.1 Withdrawal

#### 7.1.1 Premature Discontinuation of Subject in the Study

The Investigator will make every effort to keep each subject in the study. However, should a subject be removed from the study or elect to decline further study participation, the information will be recorded on the appropriate page (Final Status) in the eCRF and the

As far as possible, all examinations scheduled for the final study visit must be performed on all subjects who receive study drug but do not complete the study according to protocol.

The subject must return all unused investigational products.

Confidential Page 39 of 67

Subjects who are withdrawn from the study due to AE will be treated according to established acceptable medical practice and followed for outcome. All pertinent information concerning the outcome of such treatment will be entered in the eCRF.

The Investigator will make every effort to contact subjects lost to follow-up.

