#### 10.3 Study Populations

#### 10.3.1 Efficacy Populations

#### 10.3.1.1 ITT Population

The ITT population will be defined as all subjects who are randomized to double-blind study drug at Visit 7 and subsequently received at least one dose of study medication.

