#### 2. INTRODUCTION

This Statistical Analysis Plan (SAP) describes the planned statistical analyses to be performed for the analysis of data from Study CLR\_09\_21, "A Placebo-Controlled Randomized Withdrawal Evaluation of the Efficacy and Safety of

in Subjects with Spasticity Due to Multiple Sclerosis."

The SAP is prepared to provide a more technical and detailed elaboration of the principal statistical features stated in the protocol. The SAP will ensure that the tables, listings, and figures that will be produced and statistical methods that will be used are complete and accurate and will allow valid conclusions to be drawn. In the development of this SAP, the following documents were used:

- Protocol Number Version 7.0 Amendent 04, 16 Dec 2016
- Electronic Case Report Form (eCRF), 09 Mar 2012

The principles in the following guidance documents are followed in preparation of this SAP:

- International Conference on Harmonisation (ICH) E3 (1995): Structure and Content of Clinical Study Reports
- ICH E6 (1996): Guideline for Good Clinical Practice
- ICH E9 (1998): Statistical Principles for Clinical Trials

In the event that a discrepancy is found between the descriptions in the statistical section of the protocol and this document, the description in this document supersedes the descriptions in the statistical section of the protocol.

The responsible party at SPARC Ltd. will be required to review and approve all versions of the SAP.

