#### 5. STATISTICAL ANALYSIS GENERAL CONSIDERATIONS

#### **5.1 Analysis Populations**

#### **Safety Population:**

The safety population will be all subjects who received at least one dose of
. Subjects who discontinue having received only (in Part 1) and are not available for evaluation at Visit 2 will not be included in the safety population. The Safety Population for Part 3 will be based on only those Safety subjects who received a dose of randomized study drug at Visit 7.

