#### **Intent-to-Treat (ITT) Population:**

The ITT population will be defined as all subjects who are randomized to double-blind study drug at Visit 7 and subsequently received at least one dose of study medication, and have one subsequent modified Ashworth and CGIC score at the same assement.

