#### 6.2.1.2 Clinical Global Impressions of Change (CGIC)

Version 9.0

CGIC will be assessed at Visits 4, 7, 8, 9, 10, and 11.

The 7-point scale for CGIC is presented below:

**Scale**: Overall impression

**0** : Not assessed

1 : Very much improved2 : Much improved3 : Minimally improved

4 : No change

5 : Minimally worse6 : Much worse7 : Very much worse

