# **Figures**

Figure 14.1.2.1	Subject Disposition
Figure 14.2.20.1	Time to Dropout
Figure 14.3.5.1.1	Suicidal Ideation and Behavior Histogram – Part 1
Figure 14.3.5.2.1	Suicidal Ideation and Behavior Histogram – Part 2
Figure 14.3.5.3.1	Suicidal Ideation and Behavior Histogram – Part 3

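### SAP Table 14.2.20 describes time to dropout in a population that leaves out randomized, dosed subjects who quit Part 3 without a joint Ashworth and CGIC rating

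*SAP*

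**What the plan says.** - SAP 9.1 lists Table 14.2.20 as "Time To Dropout in Part 3 (ITT Population". The figure list has a companion, Figure 14.2.20.1, "Time to Dropout", with no population named.
- SAP 5.1 defines ITT as randomized at Visit 7 and dosed, with a further condition: "and have one subsequent modified Ashworth and CGIC score at the same assement". I call this a joint rating.
- Protocol 10.3.1.1 has no rating condition. Its ITT set is "all subjects who are randomized to double-blind study drug at Visit 7 and subsequently received at least one dose of study medication".
- The SAP's definition governs. SAP 2 states that where the two differ, "the description in this document supersedes the descriptions in the statistical section of the protocol".
- SAP 6.2.1.2 states: "CGIC will be assessed at Visits 4, 7, 8, 9, 10, and 11". Visit 8 is therefore the first scheduled joint rating after randomization at Visit 7.
- SAP 5.1 also defines a Part 3 Safety Population with no rating condition: "only those Safety subjects who received a dose of randomized study drug at Visit 7".
- Protocol 5.3 requires a withdrawing subject to go through the final-visit procedures. Protocol 7.1.1 puts the same request as best effort for subjects who do not complete: "As far as possible, all examinations scheduled for the final study visit must be performed on all subjects who receive study drug".

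**The concern.** A time-to-dropout display should have in its risk set everyone who could drop out, from the start of the period. Here entry depends on something that happens after randomization and is tied to staying: being seen and rated on both scales at least once. A subject who leaves before that has the event but is never counted as at risk.

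The interval affected most is the first week of Part 3. If unrated leaving is more common in one arm, the comparison of dropout between arms changes too. SAP 6.1.1 lists clinical worsening or loss of efficacy among the discontinuation reasons, so the timing of leaving may carry information about the treatment effect. In the readable output list, this table and its figure are the only time-to-dropout displays.

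**Working it through.** **Mechanism**

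1. Protocol 4.4.4.1 and 4.4.4.2 place Visit 7 at Day 120 ± 1 and Visit 8 at Day 127 ± 1. The gap is 127 − 120 = 7 days, or 5 to 9 days if both windows are used in full (126 − 121 = 5; 128 − 119 = 9).
2. In that gap, a subject who leaves can enter the SAP ITT set only if an exit or unscheduled visit produced both scores.
3. A subject who was dosed and left with no joint rating meets the protocol's ITT definition and belongs to the Part 3 Safety Population, but fails the SAP's ITT definition. The table omits that subject.

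**Effect on the proportion who drop out**

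The documents give no figure to reproduce. Let n be the subjects dosed in an arm, d those who drop out of Part 3, and e the dropouts with no joint rating. Assume that everyone who completes Part 3 has at least one joint rating from its four scheduled post-randomization visits.

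- All dosed subjects: d / n
- SAP ITT set: (d − e) / (n − e)
- Shortfall: d/n − (d − e)/(n − e) = e(n − d) / [n(n − e)], which is never negative and is zero when e = 0.

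The overall proportion can therefore only be understated.

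**Illustration**

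The plan is to randomize at least 240. The readable text gives neither the allocation ratio nor a Part 3 dropout rate. I assume 120 per arm, d = 6, 12 or 24, and e from 0 to 6.

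| d | All dosed | e = 0 | e = 1 | e = 3 | e = 6 |
|---|---|---|---|---|---|
| 6 | 5.0% | 5.0% | 5/119 = 4.2% | 3/117 = 2.6% | 0/114 = 0.0% |
| 12 | 10.0% | 10.0% | 11/119 = 9.2% | 9/117 = 7.7% | 6/114 = 5.3% |
| 24 | 20.0% | 20.0% | 23/119 = 19.3% | 21/117 = 17.9% | 18/114 = 15.8% |

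**Effect on the arm difference (placebo minus active, 120 each)**

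| Active d (e) | Placebo d (e) | All dosed | SAP ITT set |
|---|---|---|---|
| 6 (0) | 12 (6) | 10.0 − 5.0 = 5.0 points | 6/114 − 6/120 = 0.3 points |
| 6 (3) | 18 (6) | 15.0 − 5.0 = 10.0 points | 12/114 − 3/117 = 8.0 points |
| 12 (2) | 12 (6) | 10.0 − 10.0 = 0.0 points | 6/114 − 10/118 = −3.2 points |

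These splits are chosen to show that a difference can shrink or be created. None is a forecast.

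**The case against.** **Exit visits bring many early leavers back in.** This stands in part. The final-visit list includes both scales, and Protocol 5.3 requires it of withdrawing subjects. A reader might infer that everyone who leaves before Visit 8 is missing; the documents do not support that. Protocol 7.1.1, however, asks only for best effort and expects some subjects to be lost to follow-up, and such a subject may give no rating.

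**The excluded subjects are reported elsewhere.** This stands, and it limits the harm. SAP 6.1.1 requires Part 3 counts of subjects dispensed drug and in ITT by arm, so the number excluded can be read off by subtraction. It also requires discontinuations by arm and reason, and a CONSORT figure. Table 14.1.1.2 covers all subjects. The disposition listing covers all enrolled and records when the last dose was taken and when the subject was last contacted. A reader might infer that early dropout is concealed; it is not. What is missing is its place in the summarized time-to-event display.

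**The method text cannot be read.** SAP 6.2.3 to 6.2.4.4 is not legible in the public version, so the event, the time origin and the purpose are unknown. Part of the fix may already be there. The table title is nevertheless explicit about its population.

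**The choice may be deliberate, to match the efficacy set.** Describing dropout among the subjects in the primary analysis is coherent as a complement. It cannot stand as the only time-to-dropout display, because being rated is itself a consequence of staying.

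**The cause is the ITT definition.** Correct: adopting the protocol's definition would repair this table as well. The table still needs its own correction if the sponsor keeps the SAP set for efficacy.

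**Conclusion.** The point holds for a defined group: randomized subjects who took double-blind drug and left Part 3 with no joint rating. The time-to-dropout table omits them, so early dropout is understated whenever any such subject exists, and the arm comparison may move in either direction. The size cannot be computed from the documents and is zero if every leaver is rated. All percentages above rest on an assumed 120 per arm and assumed numbers of dropouts and unrated leavers.

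A reader might infer that more placebo subjects will leave in the first week and that the table would mask this. No readable passage gives early dropout by arm, and the schedules describe Part 3 as a down-titration phase, so that direction is not established. Nor does this label alter the primary or secondary results. Figure 14.2.20.1 names no population, so that it shares the fault is a presumption. This is a free improvement to a supportive output.

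**What to change.** 1. Run Table 14.2.20 on all randomized subjects who received double-blind drug (the Part 3 Safety Population in SAP 5.1), by arm, with time counted from Visit 7.
2. State the same population in the title of Figure 14.2.20.1.
3. Make the dropout count agree with the Part 3 discontinuations in Table 14.1.1.2, with a footnote for anyone randomized but not dosed. For this to work, the set needs one wording: SAP 5.1 bases it on having received a dose, while SAP 6.1.1 bases it on having been dispensed drug.

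The cost is a changed population label, a figure title and a footnote in the SAP and shells. The population already serves other Part 3 tables, no new data are needed, and the primary test and its alpha are untouched. If the sponsor also wants dropout within the efficacy set, that can be added as a second display.

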#### 10.4.2.1 Subject Disposition Criteria

- Number of subjects who were enrolled in each phase of the study
- Number and proportion of subjects (by treatment group and overall) who discontinued the double-blind phase prior to Visit 11.
- Number and proportion of subjects (by treatment group and overall) who dropped-out for each of the following categories for why a subject may be prematurely discontinued from the study (Section 7.1.1):
  - Dropped-Out Due to Adverse Event: Subjects who are discontinued from the study medication due to the occurrence of an AE will be recorded as dropouts. The AE will be recorded and all subjects irrespective of time of dropout (after Visit 2 and have taken one study dose) will be considered for safety analysis.
  - Dropped-Out Due to Major Protocol Violation: Subjects who are discontinued from the study due to the occurrence of a major protocol violation will be recorded as dropouts.
     The protocol violation will be recorded and all subjects irrespective of time of dropout (after Visit 2 and have taken one study dose) will be considered for safety analysis.

 Dropped Due to Other Reasons: Subjects who are discontinued from the study due to any other reason will be recorded as dropouts. The reason for discontinuation will be recorded all subjects irrespective of time of dropout (after Visit 2 and have taken one study dose) will be considered for safety analysis.

Subjects who drop out after Visit 1 will not be replaced (Section 7.2).

Confidential Page 55 of 67

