During the course of the study, subjects will be monitored for adverse events and vital signs (seated blood pressure, pulse, respiration, and body temperature) measured at each clinic visit. Suicidality will be assessed at every visit using the Columbia – Suicide Severity Rating Scale (C-SSRS). Clinical laboratory testing will be repeated at the end of the open-label phase,

after all subjects have received a fixed-dose and if needed, at Visit 11 (Week 22)

or early termination. ECGs will be recorded at screening, after subjects have completed the run-in (Visit 2), after subjects have received

for 6 weeks (Visit 4), after subjects have received

for 18 weeks (Visit 7), and if needed, at Week 22 (Visit 11) or early termination. Physical and neurological evaluation will be performed at screening and if needed, at Week 22 (Visit 11) or early termination.

At the final visit clinical laboratory testing, ECG measurement, and physical and neurological evaluation will be performed if needed. Any treatment-emergent abnormalities shall continue to be evaluated with testing as needed to follow resolution.

Subjects will be instructed that even though they may have extra medication, they should return to the clinic for their visits according to the schedule of events.

Subjects who enter the double-blind randomized withdrawal phase (Part 3) will be offered the opportunity to participate in a separate open-label trial

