### 6.1 Study Subjects

### 6.1.1 Subject Disposition

The final study disposition of each subject will be captured in the eCRF. For those subjects who do not complete the study as planned, all potential reasons for discontinuation should be provided, with one indicated as primary. The reasons for discontinuation will be categorized as described below and the following descriptive summaries of study disposition will be provided.

- Number of subjects who were enrolled in each phase of the study (Part 1, Part 2, Part 3):
  - o Part 1: Received at Visit 1
  - o Part 2: Received at Visit 2 (Safety Population)
  - o Part 3:
    - Randomized at Visit 7
    - Dispensed Blinded Study Drug at Visit 7 (Safety Population Part 3) by treatment group and overall
    - Intent-to-Treat Population by treatment group and overall
    - Per Protocol Population by treatment group and overall
- Number and proportion of subjects (overall for Parts 1 and 2 and by treatment group and overall for Part 3) who discontinued each phase of the study.
- Number and proportion of subjects (overall for Parts 1 and 2 and by treatment group and overall for Part3) who dropped-out for each of the following categories (based on primary reason and also based on all reasons) for why a subject may be prematurely discontinued from the study.

- Withdrew Consent
- Adverse Event
- MS-related Disease Progression

0

- Required Dose Change Between Visit 4 and Visit 11
- Major Protocol Deviation
- Lost to Follow-up
- Worsening of Clinical Condition or Loss of Efficacy
- o Withdrew, Per Sponsor
- o Withdrew, Per Investigator
- Other

A listing of subject disposition will be prepared, inclusive of dates of last dose and last contact, and any investigator comments regarding reason for discontinuation. A summary table will tabulate overall disposition of the subjects by the categories above. A CONSORT figure will summarize subject disposition.

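### The Part 1 C-SSRS table uses a Safety Population defined by reaching Part 2, so subjects who left during Part 1 are missing from it

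*SAP*

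**What the plan says.** SAP 9.1 lists Table 14.3.5.1 as "C-SSRS Summary of Suicidal Ideation and Suicidal Behavior in Part 1" and labels it Safety Population. The matching histogram, Figure 14.3.5.1.1, carries no population label.

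The Safety Population is set out in three places:

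- SAP 5.1 opens with "The safety population will be all subjects who received at least one dose of" a drug whose name is blacked out. It then says that subjects who stop after receiving only the Part 1 treatment "and are not available for evaluation at Visit 2 will not be included in the safety population".
- SAP 6.1.1 counts Part 1 by receipt at Visit 1, and attaches the population label only to Part 2, for those who received drug "at Visit 2 (Safety Population").
- Protocol 10.4.2.1 agrees: dropouts who left "after Visit 2 and have taken one study dose) will be considered for safety analysis".

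On data collection, SAP 3.2 states: "Suicidality will be assessed at every visit using the Columbia" scale. The schedules in both documents mark C-SSRS at Screening, Visit 1 and Visit 2. SAP 6.3.7 plans frequencies at baseline and during the trial and names no population. C-SSRS Listings 16.2.13.1 to 16.2.13.4 say Safety Population in their titles and All Enrolled in their population column.

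**The concern.** A table that describes Part 1 should cover the subjects treated in Part 1. This one covers those who got past it. Membership depends on something that happens after the period being described, so anyone who left before Visit 2 drops out of both numerator and denominator, whatever the reason for leaving.

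For suicidality the reason for leaving can be the outcome itself. If a subject left Part 1 because of suicidal ideation or behavior and was assessed on leaving, that result would exist in the database but could not appear in the Part 1 summary.

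**Working it through.** The plan states no figure on this point, so there is nothing to reproduce. The check is on definitions, followed by an illustration of scale.

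**Who is in the table.** The drug name in the SAP 5.1 inclusion rule is blacked out, but SAP 6.1.1 ties the Safety Population to receipt at Visit 2 and counts receipt at Visit 1 separately. Read together, a subject who took only Part 1 medication is outside the population. The explicit exclusion sentence in SAP 5.1 is narrower, because it adds the condition of not being available at Visit 2. A subject who attends Visit 2 but takes no Part 2 drug is excluded by the dosing rule, though not by that sentence taken alone.

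**Whether the omitted subjects can have data.** They can. C-SSRS is scheduled at Screening and Visit 1, before any Part 1 departure. Protocol 5.3 asks a withdrawing subject to undergo the final-visit procedures. Protocol 7.1.1 asks for them, as far as possible, in subjects who received study drug and did not complete. The Visit 11 procedures in Protocol 4.4.4.5 include C-SSRS.

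**Whether another summary fills the gap.** The AE and SAE tables in SAP 9.1, including fatal SAEs, cover Parts 2 and 3 only. Protocol 10.4.5.1 says pre-treatment events are to be summarized separately, whereas SAP 6.3.1 only flags them in a listing. No other planned table summarizes clinical events in Part 1 alone.

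**Scale, by assumption.** Inputs from the documents are about 300 enrolled and at least 240 randomized. Planned attrition over Parts 1 and 2 together is then at most about 300 − 240 = 60, or 60/300 = 20%. The Part 1 share is not given. Let x be the number who leave before dosing at Visit 2. Assume that all 300 took Part 1 medication and that everyone in the Safety Population has C-SSRS data.

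| x (assumed) | Share of 300 | Subjects in the table as planned, 300 − x |
|---|---|---|
| 3 | 1% | 297 |
| 15 | 5% | 285 |
| 30 | 10% | 270 |
| 60 (all attrition falls in Part 1) | 20% | 240 |

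Suppose further that one leaver had an event recorded on C-SSRS and that no one else did. The planned table would show 0 out of 300 − x. On the Visit 1 treated set the result would be 1/300 = 0.33% if every leaver was assessed. If only that leaver was assessed, it would be 1/(300 − x + 1): 1/298 = 0.34% for x = 3 and 1/271 = 0.37% for x = 30. The documents give no basis for the probability of such an event, so these figures show only what a single case would do.

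**The case against.** The strongest defence is that the choice is deliberate and consistent. The Safety Population is built around the drug given in Part 2, run-in events are treated as pre-treatment, and the exposure and compliance tables for Parts 1 and 2 use the same population. That justifies the population for Parts 2 and 3. It does not make it suitable for a table whose stated scope is Part 1.

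Second, many omitted subjects may have little to contribute. Visit 2 is the scheduled assessment that captures the Part 1 week, and assessment on leaving may not always be achieved. SAP 6 bases percentages on subjects with non-missing data, so an unassessed leaver would not enter an on-treatment denominator under any label. This stands, and it limits the gain to leavers who were assessed.

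Third, the information is not lost altogether. Table 14.1.1.2 covers all subjects, and SAP 6.1.1 reports Part 1 discontinuations by reason. The AE and SAE listings are All Enrolled. This also stands. The C-SSRS listings are less secure cover, because their titles and population column disagree.

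A reader might go further in three ways that the documents do not support:

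- That Part 1 leavers are the subjects most likely to have had an event. This is plausible, but nothing in either document states or quantifies it.
- That Part 1 is the reference against which Parts 2 and 3 are judged. SAP 6.3.7 plans frequencies only, with no comparison between parts, and Part 3 has its own randomized placebo group.
- That a death before reassessment would appear once the label is changed. Such a subject has no later C-SSRS form; the event would be found through SAE reporting and the All Enrolled SAE listing.

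**Conclusion.** The point holds as a minor fault in the specification of one descriptive safety table. Table 14.3.5.1 reports Part 1 on a population defined by reaching Part 2, so subjects who received only Part 1 medication and left before Visit 2 are absent from the only planned summary table of suicidality in that part. This rests on reading the blacked-out drug in SAP 5.1 as the one received at Visit 2, which SAP 6.1.1 and Protocol 10.4.2.1 support.

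The size of the effect cannot be determined: the documents give neither a Part 1 dropout number nor an event rate among leavers. It is zero if no assessed leaver had an event. The documents do not show that Part 1 will look safer than it was, only that the table could not show such a case. Efficacy and the randomized Part 3 safety comparison are unaffected.

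**What to change.** - Base Table 14.3.5.1 on all subjects who received Part 1 medication at Visit 1, a set that SAP 6.1.1 already counts. Use as denominators the subjects with C-SSRS data, and show that number.
- State the same population on Figure 14.3.5.1.1.
- Reconcile the titles of Listings 16.2.13.1 to 16.2.13.4 with their population column, so that C-SSRS data from Part 1 leavers are listed.
- Keep the Safety Population for the Part 2 and Part 3 tables.

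The cost is a population label and denominator for one table, a label for one figure and four listing titles. No new data are needed, and no other analysis changes.
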